7.10.6 Plasma HIV-1 RNA level and TruCount T Assay

- Frequency of testing: At Treatment Visits 2, 4, 6, 8, 10, 12, 14, 16, 18, 20, 22, 24, 26, 28, 30, 32, 34, 36, 38, 40, 42, 44, 46, 48, 50, 52, 54, 56 and 58. Beyond TE60, blood sample will be collected at least once every four weeks, at EOT, at VF, and at VF-EFU and NVF-EFU visits.
- To assess antiretroviral therapeutic response to PRO 140

Note: *Plasma HIV-1 RNA level will be measured using Human Immunodeficiency Virus 1 (HIV-1), Quantitative, RNA (Abbott RealTime) test.*

TruCount T Assay includes measurement of Absolute Lymphocytes, CD3 cell count, CD4 cell count, CD8 cell count, CD3%, CD4% and CD8%

7.10.7 Anti-idiotypic antibodies to PRO 140

- Frequency of sample collection*: At first Screening Visit, at Treatment Visits 4, 8, 12, 16, 20, 24, 28, 32, 36, 40, 44, 48, 52 and 56. Beyond TE60, ADA sample for PRO 140 assessment will be performed once every four weeks. Sample also collected at VF, NVF-EFU2 and VF-EFU1 visits.

***Note:** *Sera will be collected from study subjects and stored at -80°C for future analysis.*

7.10.8 Trofile® RNA or Trofile® DNA and PhenoSense® Entry Assay (Trofile® with enhanced sensitivity)

- Frequency of testing: At EOT and at the time of virologic failure
- Trofile® RNA is a phenotypic viral RNA assay to assess any change in HIV-1 co-receptor tropism.
- Unlike the standard Trofile® RNA assay, which uses viral RNA found in the plasma of patients with viral loads ≥ 1000 copies/mL, Trofile® DNA uses viral DNA extracted from cells in a whole blood draw is a phenotypic viral RNA assay to assess any change in HIV-1 co-receptor tropism. PhenoSense® Entry is a phenotypic viral RNA assay to assess resistance of HIV-1 RNA virus to entry inhibitors

7.10.9 HIV Genotyping Assay

- Frequency of testing: At the time of virologic failure
- To identify reverse transcriptase (RT), protease (Pr) and gp120 gene mutations associated with current or evolving drug resistance.

7.10.10 Serum Concentration of ART drugs

- Frequency of testing: At Treatment Extension Visits 4, 8, 12, 16, 20, 24, 28, 32, 36, 40, 44, 48, 52, 56, and at least once every four weeks for the rest of the treatment phase starting at Treatment Visit 60.
- To confirm that enrolled subjects are abstaining from taking their previous ART regimen during the monotherapy treatment phase.

7.10.11 Blood sample collection for Exploratory/Confirmatory analysis

- Frequency of testing: At second Screening Visit, at interim treatment visits, EOT and at the time of virologic failure
- CytoDyn is currently investigating the possibility of developing a more accurate test for detection of co-receptor tropism in patients with undetectable viral loads and in case of early breakthrough/virologic failure during the treatment phase of the study, in addition to assessing viral load reduction efficacy with alternate plasma HIV-1 RNA assays.

7.10.12 CCR5 Receptor Occupancy

CCR5 Receptor Occupancy

- To assess the number CCR5 receptors on patients' CD4 cell surface. Of those CCR5 receptors, the test will also assess the number and percentage of CCR5 receptors that are covered by PRO 140.
- Frequency of testing: This assessment will be performed up to 5 times at different treatment visits. Blood will be taken prior to PRO 140 injection (trough sample) and 24-48 hours (peak sample) after the PRO 140 injection to check for CCR5 occupancy, and correlative analysis will be performed with PRO 140 PK concentration and HIV-1 RNA levels.

All laboratory reports will be reviewed by the Investigator.

Post-treatment abnormal results that are considered by the Investigator to be clinically significant will be recorded as adverse events. If the Investigator judges it necessary, testing may be repeated in order to make the determination of clinical significance. Validated, quality-controlled laboratory data will be transferred to the main database for analyses.

7.11 PRO 140 ADMINISTRATION

Refer to [Section 6.4](#) for details.

[figure not shown]
7.12 INJECTION SITE REACTION ASSESSMENT

At each visit during the Treatment Extension Phase, an injection site reaction assessment will be made for the current and previous injection sites. Injection site reaction assessments are recorded by the Investigator starting after the first injection is given. Injection site reaction assessments will not be completed when subjects perform self-administration. Refer to [sections 9.1.8](#) and [17.3](#) for more details.

7.13 PAIN ASSESSMENT USING VISUAL ANALOG SCALE (VAS)

Tolerability of repeated subcutaneous administration of PRO 140 is evaluated based on assessment of subject-perceived injection site pain using the Pain Visual Analog Scale (VAS).

Beginning at Screening Visit 1, subjects will be asked to mark the point that best represents the average pain intensity **over the past week** at the injection site on a horizontal line (100 mm in length) anchored by the following word descriptors at each end, "no pain" on the left side and "pain as bad as it could possibly be" on the right side of the line. The subject marks on the line or by pointing to a position on the line the point that they feel represents their perception of their pain state. The VAS score is determined by measuring in millimeters from the left-hand end of the line to the point that the patient marks.

Figure 7-1: Visual Analog Scale

7.14 COVID-19 GUIDANCE

The purpose of this guidance is to inform sites how to proceed in light of the challenges faced by patients and clinical trial sites as a result of COVID-19 shelter-in-place mandates from state governments. The content of this letter is based on FDA Guidance on Conduct of Clinical Trials of Medical Products during COVID-19 Pandemic (18 Mar 2020).

- The current schedule of assessments requires subjects to visit the clinic at least once every four weeks for lab assessments. Subjects may still continue to receive treatment with PRO 140 if they are unable to visit the clinic.
- Site staff may visit subjects' homes to conduct study assessments and/or deliver PRO 140.
- Sites may ship PRO 140 to subjects' homes if subjects are unable to visit the clinic.
- If subjects are unable to visit the clinic at least once every four weeks lab assessments will be missed. If this occurs site staff should contact subjects weekly by phone to assess:
 - Compliance to study treatment
 - Potential adverse events
 - Changes in concomitant medications
- Sites should document phone calls and include confirmation of compliance to study treatment and report any adverse events and/or changes in medications.
- Subjects who report positive tests results for COVID-19 should have the diagnosis recorded as an adverse event.
- Sites should clearly document reasons for failing to obtain required assessments (e.g., limitation imposed by COVID-19 leading to the inability to perform the protocol-specified assessment).

- Any changes in the study visit schedule or missed visit should be entered as protocol deviation in the EDC and reason should be documented as missed study visit or visit performed out of window period due to COVID-19.
- If subject is early withdrawn from the study due to COVID-19, the reason should be clearly documented in the End of Study (EOS) section in EDC as “study discontinuation due to COVID-19”.
- Monitoring activities will be performed remotely until Centers for Disease Control (CDC) recommendations allow travel to resume.

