1.7 RISKS / BENEFITS ASSESSMENT

1.7.1 RISKS/DISCOMFORT TO SUBJECTS AND PRECAUTIONS TO MINIMIZE RISK

1.7.1.1 Risks associated with Temporary Discontinuation of current Antiretroviral Treatment Regimen

The study treatment (PRO 140 monotherapy) may not be effective in maintaining the viral suppression for all subjects. In such cases, temporary discontinuation of antiretroviral therapy could lead to a rebound in viral load and might be associated with an increase risk of developing drug resistance, opportunistic infections and clinical progression of the disease.

Study participants will be regularly monitored for viral rebound following initiation of PRO 140 monotherapy and will re-initiate their previous antiretroviral regimen if plasma HIV-1 RNA levels rise up to or above 400 copies/ml on two consecutive blood draws at least 3 days apart.

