4.2 TREATMENT EXTENSION PHASE

Treatment Extension Phase begins with an evaluation of results of laboratory samples collected during the Screening Phase. Subjects who meet all eligibility criteria, as per data gathered from Screening Phase are to be treated. All subjects who fail to meet eligibility criteria will be considered screen failures, exit the study without further evaluation and enter the Follow-up Phase of the PRO 140_CD 01 Treatment Substitution protocol.

Eligible subjects will receive PRO 140 weekly SC treatments, given every week (\pm 3 days) or until virologic failure, whichever occurs first.

PRO 140 will be administered as a 350 mg subcutaneous injection weekly. The study treatment (PRO 140 SC injections) will be administered by a qualified medical professional (MD, DO, PA, LPN, LVN, NP, RN, or CMA if permitted by state law) or subjects trained to perform self-administration of study treatment (see [section 6.4](#)).

Note: Patients enrolled under a previous Protocol (V.1.0-9.0) have the option of increasing their dose to receive 700mg weekly for the remainder of the Treatment Extension Phase.

All study subjects will re-initiate their previous antiretroviral regimen:

- One week prior to the end of Treatment Extension Phase, or
- Anytime during the Treatment Extension Phase, if virologic failure occurs or have met any other criteria for discontinuation of study treatment as specified in [section 5.2.1](#) of the protocol.

Note:

- In case of increase in plasma HIV-1 RNA levels above 200 copies/mL, subjects will return to clinic for another blood draw in-between the Treatment Visits for repeat plasma HIV-1 RNA levels, as per the discretion of the Investigator.
- Subjects who experience virologic failure (defined as two consecutive HIV-1 RNA levels of \geq 400 copies/ml separated by at least 3 days) at any time during the Treatment Extension Phase will undergo the Virologic Failure (VF) Visit assessments and enter the Follow-up Phase of the study.
- Subjects who meet any criteria (other than virologic failure) for discontinuation of study treatment as specified in [section 5.2.1](#) of the protocol, will undergo TE161 Visit assessments and enter the Follow-up Phase of the study.
- Subjects who do not experience virologic failure will enter the Follow-up Phase of the study at the end of 161-week Treatment Extension Phase.

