4.2.3 Treatment Visit-60 (TE60) onwards – Monthly Visits

Patients are required to have a clinic visit at least once every four weeks from TE60 onwards. Subjects will re-initiate previous antiretroviral regimen at end of treatment extension phase (one week prior to last PRO 140 treatment), if viral load remain suppressed.

The following assessments will be performed at every clinic visit:

- Assess for any Adverse Events and changes in Concomitant medications (see [section 9](#) and [7.5](#)),
- Symptom-directed physical examination (see [section 7.6](#)),
- Neurological Assessment (see [section 7.7](#))
- Vital Signs (see [section 7.9](#))
- **Note:** *Vitals not obtained when subject self-administers study treatment outside clinic*
- Study Treatment Administration (PRO 140)
- **Note:** *Subjects trained to perform self-administration of study treatment may self-administer when clinic visit not required (no lab sample collection needed)*

- Injection Site Reaction Assessment (see [section 7.12](#))
 - **Note:** *To assess injection site reactions, the investigator will use the DAIDS AE grading table (see [section 17.3](#)).*
 - **Note:** *Assessment will be performed when subject administered study treatment at clinic visit*
- Subject-perceived Injection Site Pain Assessment (see [section 7.13](#))
 - **Note:** *Subject-perceived injection site pain will be assessed using the Pain Visual Analog Scale (VAS) prior to study treatment administration assessing average pain at injection site since last treatment.*
 - **Note:** *Performed at the time of clinic visit.*
- Collection of Blood Specimens (see [section 7.10](#)) for
 - Plasma HIV-1 RNA level
 - TruCount T Assay
 - Routine CBC
 - Biochemistry
 - PK sample for PRO 140
 - Serum concentration of ART drugs
 - Anti-idiotypic antibodies to PRO 140
 - Blood sample for exploratory analysis
- **Note:** *Trofile® RNA or Trofile® DNA and PhenoSense Entry Assay will be performed at the last treatment visit (EOT)*
 - CCR5 Receptor Occupancy
- **Note:** *Blood will be taken prior to PRO 140 injection (trough sample) and 24-48 hours (peak sample) after the PRO 140 injection to check for CCR5 occupancy, and correlative analysis will be performed with PRO 140 PK concentration and HIV-1 RNA levels. This assessment will be performed up to 5 times at different treatment visits.*

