5.2.1 Discontinuation of Study Treatment

Discontinuation of study treatment and resumption of previous antiretroviral therapy is recommended if:

- Subject experiences virologic failure (defined as two consecutive HIV-1 RNA levels of ≥ 400 copies/ml separated by at least 3 days)
- Develops retroviral rebound syndrome or AIDS-defining conditions as specified in Appendix I ([Section 17.1](#)).
- Shows signs or symptoms of clinically significant immunosuppression
- Subject or the subject's clinician wishes to restart ART.
- Subject becomes pregnant.

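### Section 7.14 lets PRO 140 monotherapy continue through missed HIV-1 RNA samples with no limit on the gap, so the virologic restart rule cannot act on asymptomatic rebound

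*Protocol*

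**What the plan says.** Under normal conduct, section 4.2.3 sets the minimum contact: "Patients are required to have a clinic visit at least once every four weeks from TE60 onwards". Section 7.10.6 ties HIV-1 RNA sampling to the same four-weekly minimum.

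Section 1.7.1.1 names the safeguard for subjects off ART. They are monitored regularly and are to "re-initiate their previous antiretroviral regimen if plasma HIV-1 RNA levels rise up to or above 400 copies/ml on two consecutive blood draws". The two draws must be separated by 3 days or more. Section 5.2.1 uses the same virologic criterion. Section 4.2 adds an earlier warning step, left to the Investigator's discretion: "In case of increase in plasma HIV-1 RNA levels above 200 copies/mL, subjects will return to clinic for another blood draw".

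Section 7.14 then covers subjects who cannot attend:

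- PRO 140 may continue, and "Sites may ship PRO 140 to subjects' homes if subjects are unable to visit the clinic".
- "Site staff may visit subjects' homes to conduct study assessments and/or deliver PRO 140". This is permissive and does not name a blood draw.
- "If subjects are unable to visit the clinic at least once every four weeks lab assessments will be missed". In that case staff phone weekly about treatment compliance, adverse events and concomitant medications.
- The reason for a missed assessment is documented, and a missed visit is entered as a protocol deviation.

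**The concern.** Both virologic rules need a blood sample. Section 7.14 allows sampling to lapse while dosing continues, and it gives no point at which someone must obtain a sample or decide whether to go on. A site that follows it exactly can keep a subject on monotherapy, without ART and without a viral load, for as long as attendance is impossible. The same applies after a first value of 400 copies/mL or more, because nothing in 7.14 makes the confirmatory draw a priority.

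The subject's safety is at stake. Section 1.7.1.1 itself lists drug resistance, opportunistic infection and clinical progression as risks of rebound. Section 1.6 states that most subjects on 350 mg weekly monotherapy in the CD03 study had virologic failure, and 350 mg is still an allowed dose here (section 8.1). DMC review of virologic rebounds (section 12) also depends on samples being taken.

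**Working it through.** The plan gives no figure for this point, so there is none to reproduce. The check has two parts.

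**1. Is there a limit anywhere?** Sections 4.2, 4.2.3, 5.2, 5.2.1, 7.10.6, 7.14 and 11.4 were read for a maximum time without an HIV-1 RNA result, a mandatory home or local draw, or an action triggered by a missing result. None has one. The stop routes that do not need a viral load are:

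- 5.2.1: rebound syndrome, an AIDS-defining condition, signs of immunosuppression, pregnancy, or the wish of the subject or clinician to restart ART.
- 5.2: Investigator discontinuation when medically necessary, and possible withdrawal for a major protocol violation.
- 11.4: the sponsor decides on continuation after a deviation.

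Each needs symptoms, an unrelated event or someone's initiative. None detects viraemia without symptoms.

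**2. How late can detection be?** The only input is the four-weekly interval (4.2.3, 7.10.6). Let m be the number of consecutive draws missed.

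- Time between results = 4(m + 1) weeks.
- Take a rebound in the interval after draw j (j = 0 is the last sample obtained; j runs from 0 to m − 1). The schedule would sample it at week 4(j + 1). It is actually sampled at week 4(m + 1).
- Extra delay = 4(m + 1) − 4(j + 1) = 4(m − j) weeks. The maximum is 4m, at j = 0.
- If rebound is equally likely in each of the m intervals, the mean is 4(m + 1)/2 = 2(m + 1) weeks.

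| Missed draws m | Weeks between results | Maximum extra delay (weeks) | Mean extra delay (weeks) |
|---|---|---|---|
| 1 | 8 | 4 | 4 |
| 2 | 12 | 8 | 6 |
| 3 | 16 | 12 | 8 |

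Rebounds in the last 4 weeks of a gap are left out, because the normal schedule would not have sampled them sooner. The ±3-day visit window is ignored. Confirmation at least 3 days later is needed with or without a gap, so it does not change the difference. The result needs no rebound rate. Under 7.14 as written, m has no upper bound.

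**Primary comparison.** Subjects enter after 12 weeks of CD01 treatment (12 × 7 = 84 days). The four-weekly schedule starts at TE60, which is 59 × 7 = 413 days after TE1. A gap in that schedule therefore falls beyond day 30 on either time origin.

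**The case against.** Section 7.14 does not waive monitoring. It restates the four-weekly requirement, lets staff perform assessments at home and treats a missed visit as a deviation. The weekly call is more frequent contact than the four-weekly visit, and the Investigator, the subject's clinician and the sponsor can all act. The section says it follows FDA pandemic guidance, and the DMC charter is not shown. The available data are also reassuring. CD01 failures with laboratory data re-suppressed on ART (1.5.2.7), section 1.6 reports no loss of susceptibility or change in tropism at 350 mg, subjects here already passed 12 weeks without failure, and 700 mg is an option.

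This keeps the point minor, but it does not supply the missing limit. The home draw is optional, the other routes do not detect asymptomatic rebound, and the re-suppression data come from subjects under scheduled monitoring. The FDA guidance is not at hand, so it supports neither side.

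A reader might infer more than the text supports:

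- *Nearly everyone would rebound within a 12-week gap.* Section 1.3 reports almost all subjects above 500 copies/mL by 10 weeks, but after treatment interruption in a vaccine trial, not on PRO 140.
- *Most subjects here would fail, as in CD03.* That is another study, in subjects not selected for 12 weeks of prior success.
- *The primary result is biased.* The 30-day comparison is not affected. Failures that arise in a gap would only be dated later.

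**Conclusion.** The point holds as a gap in a conduct rule that the protocol itself fixes; it is not something left to the SAP. Section 7.14 suspends the rebound safeguard of 1.7.1.1 with no end point while the exposure continues. Detection of an asymptomatic rebound is delayed by up to 4m weeks for m missed draws, and m is unlimited.

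The size rests only on the four-weekly schedule; the mean delays also assume that rebound is equally likely in each interval. The document gives no rebound rate for this selected population and no frequency of missed visits, so neither a number of affected subjects nor an expected harm is claimed. Continued dosing and home shipment in a lockdown are not themselves at fault. This is a change that the sponsor could make, not one on which the trial's conclusions depend.

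**What to change.** Add a paragraph to section 7.14 with these elements:

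1. If a scheduled four-weekly HIV-1 RNA sample is missed, a home or local-laboratory sample is obtained before the next one is due, for example no more than 8 weeks after the last sample. The sponsor may justify another limit.
2. If it is not obtained, the Investigator and Medical Monitor document a decision before the home supply runs out. They either re-initiate ART under 5.2.1, with the one-week PRO 140 overlap (7.5.1), or continue once only, to a fixed date for the next sample.
3. If that date also passes without a sample, ART re-initiation is recommended as a ground under 5.2.1. Section 4.2 already covers subjects who stop for reasons other than virologic failure: they "will undergo TE161 Visit assessments and enter the Follow-up Phase of the study".
4. After a value of 400 copies/mL or more, the confirmatory draw, at least 3 days later, is arranged promptly at home or locally. If it cannot be obtained before supply ends, PRO 140 is still supplied until ART is re-initiated, so that no subject is without both.

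If the sample is obtained by week 8, m = 1 and the extra delay is up to 4 weeks. If the single continuation is used and its date is set four weeks later (an assumption), a sample then means m = 2 and up to 8 weeks. This is a bound only if the recommendation is followed, because the lead-in of 5.2.1 is advisory: "Discontinuation of study treatment and resumption of previous antiretroviral therapy is recommended if".

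The costs are the logistics of home or local draws, Medical Monitor time, an occasional extra confirmatory draw (the repeat in 4.2 is now discretionary), and some suppressed subjects returning to ART for purely logistic reasons.

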8 STATISTICAL CONSIDERATIONS

This section presents general information about statistical considerations and concepts such as statistical power, sample size, and a brief discussion on analysis methodology, as well as some data conventions. Detailed descriptions of the statistical analysis methods and data conventions that will be used in this study will be in a separate document; i.e., the Statistical Analysis Plan (SAP).

8.1 TREATMENT GROUPS

This is a single active arm study. All eligible subjects in the study will receive PRO 140 as a 350 mg subcutaneous injection weekly and have the option of increasing their dose to receive 700mg subcutaneous injections weekly.

8.2 DESCRIPTION OF STUDY ENDPOINTS

8.2.1 Primary Efficacy Endpoints

The primary efficacy endpoint for this study is time to virologic failure after initiating PRO 140 monotherapy.

Virologic failure is defined as two consecutive HIV-1 RNA levels of ≥ 400 copies/ml separated by at least 3 days.

8.2.2 Secondary Efficacy Endpoints

- Proportion of participants with virologic failure after initiating PRO 140 monotherapy.
- Mean change in viral load (HIV-1 RNA levels)
- Mean change in CD4 cell count
- Change in quality of life metrics (up to TE107)

8.2.3 Safety Endpoints

Safety measurements will include:

- Tolerability of repeated subcutaneous administration of PRO 140 as assessed by study participants (using Visual Analogue Scale) and by investigator-evaluation of injection site reactions.
- Frequency of Grade 3 or 4 adverse events as defined by the DAIDS Adverse Event scale
- Frequency of Treatment-emergent serious adverse events

